8.2 Secondary Efficacy Endpoints

The following secondary efficacy endpoints will be analyzed using the same analysis as the primary analysis for the ITT population:

- Erythrocyte membrane composition (%) of total DHA
- Erythrocyte membrane composition (%) of total EPA
- Erythrocyte membrane composition (%) ratio of omega-6 to omega-3 fatty acids
- Plasma concentration of total DHA concentration (μg/mL)
- Plasma concentration of total EPA concentration (µg/mL)
- Plasma concentration of total DHA+EPA concentration (µg/mL)
- Plasma composition (%) ratio of omega-6 to omega-3 fatty acids

The following secondary endpoints will be repeated by age subgroups and CRFD subgroups separately.

- Erythrocyte membrane composition ratio of omega-6 to omega-3 fatty acids
- Plasma concentration of total DHA+EPA concentration (μg/mL)
- Plasma composition ratio of omega-6 to omega-3 fatty acids

8.3 Exploratory Efficacy Endpoints

The values for the following endpoints will be analyzed using the same MMRM comparing baseline to Day 90 on the ITT population as described in Section 8.1.

- Serum protein concentration (total protein, pre-albumin, albumin, transferrin)
- Plasma concentration of fat soluble vitamins (A, D and E)
- Urinary leukotriene E4 (LTE4)

The analysis for plasma concentration of vitamins A, D, and E will also be repeated by age subgroups.

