The overall objective of the study is to assess safety and tolerability and demonstrate improved fat absorption with sustained use of Relizorb in patients with CF who have EPI and are receiving enteral nutrition as part of their total nutritional therapy. In this study, subjects will be receiving a semi-elemental formula containing pre-hydrolyzed protein that has a high content of long chain triglycerides (Impact® Peptide 1.5) and will be using Relizorb during their enteral feeding in place of other therapies currently used to aid in fat digestion and absorption, such as pancreatic enzyme replacement therapy (PERT). Plasma concentration of long-chain polyunsaturated fatty acids (LCPUFAs) such as docosahexaenoic acid (DHA; C:22:6n-3) and eicosapentaenoic acid (EPA; C20:5n-3) will be measured as biomarkers of fat absorption. Tissue accretion of LCPUFAs assessed through measurement of erythrocyte membrane concentrations of LCPUFAs such as DHA and EPA, as well as determination of the profile of fatty acids in plasma will also be evaluated as additional biomarkers of fat absorption. Plasma fat-soluble vitamin and serum protein concentrations will also be measured as indicators of effectiveness. All fatty acid, fat-soluble vitamin, and protein concentrations will be assessed in relation to values obtained at the beginning of the run-in period (Day -7), at baseline (Day 0), and during Relizorb use (Days 30, 60, and 90). Safety and tolerability of sustained use of Relizorb will be assessed during use and compared with gastrointestinal symptoms recorded during the observation phase of the study (Day -14 through Day -7).

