LCTs, are pre-hydrolyzed *ex-vivo* just before ingestion and provided in a form readily available for absorption in individuals who lack pancreatic lipase or the physiological capacity to digest fat.

The objectives of this study are as follows:

- Demonstrate that sustained use of Relizorb in conjunction with enteral tube feeding without concomitant use of PERT results in an increase in fat absorption as evidenced by increased plasma concentrations of LCPUFAs such as DHA and EPA, tissue accretion (RBC) of omega-3 fatty acids such as DHA and EPA, and increased concentrations of fat soluble vitamins;
- Show that serum protein levels are maintained despite withdrawal of PERT use associated with enteral tube feeding with sustained use of Relizorb in conjunction with enteral tube feeding using a semi-elemental formula;
- 3. Demonstrate the safety and tolerability of sustained use of Relizorb in conjunction with enteral tube feeding;
- 4. Explore the potential immunomodulatory effect of increased plasma concentrations of DHA and EPA as evidenced by changes in the omega-6 to omega-3 fatty acid ratio and urinary leukotriene concentrations.

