## 7.8 Efficacy Analysis

The measurement of the absorption of fats is an important efficacy endpoint, using absorption of fatty acids as surrogate biomarkers for fat absorption. LCPUFA plasma concentrations such as DHA and EPA will be an outcome variable, along with tissue accretion of LCPUFAs, measured as relative levels in erythrocyte membrane, and the profile of fatty acids in plasma. The fatty acid profile will also be used to calculate the ratio of omega-6 to omega-3 fatty acids, another outcome variable. Fat-soluble vitamin (A, D, and E) concentration is an additional efficacy endpoint and will be used as a laboratory outcome variable. Serum protein (total protein, prealbumin, albumin, and transferrin) concentrations and urinary leukotriene concentrations are additional endpoints and also represent laboratory outcome variables.

For all laboratory outcome variables, mean values from samples obtained on Day -14 and Day 0 will be compared using a two-sided test for comparison. The mean value from samples obtained on Day 0 will be used as the baseline for comparison with mean values from samples obtained on Days 30, 60, and 90 using ANOVA.

Body weight, height, and BMI are endpoints and clinical outcome variables. Absolute change in body weight from Day 0 through Days 30, 60, and 90 will be analyzed using ANOVA. To evaluate the effect of Relizorb use on weight and BMI, up to 4 weight and BMI recordings obtained from the medical record at 3 month intervals over the previous 12 months. The historical weight recordings will be used to calculate historical weight gain velocity, expressed as grams of body weight per kilogram of body weight per day. The study weight gain velocity will be similarly calculated by using the body weight values obtained on Days 0, 30, 60, and 90. The historical weight gain velocity will be compared to the study weight gain velocity using a two-sided test for comparison. In addition, the historical weight and BMI recordings, along with the weight and BMI values recorded on Day 0, will be used to calculate a standard score for weight and BMI values recorded on Days 30, 60, and 90.

Title: Absorption and Safety with Sustained Use of Relizorb™ Evaluation (Assure) Study in Patients With Cystic Fibrosis Receiving Enteral Feeding

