## 11.0 APPENDICES

# 11.1 Peptamen® 1.5 Nutrition Information - *Unflavored* (Nestle Health Science)

One bottle equals 250 mL (1Carton) Amount Per Serving Unit Amount **Amount per Serving** Unit Amount Calories 375 Total Fat \* 14 Kcal g 255 Sodium mg (mEq) Potassium mg (mEq) 465 (12) (11.1)46 Total Carbohydrate G Protein 17 g Vitamin A\*\* IU 1615 Vitamin C 128 mg Calcium 250 Iron 6.75 Mg mg Vitamin D IU 200 Vitamin E IU 11.3 Vitamin K 30 **Thiamin** 0.75 Mcg mg Riboflavin 0.9 Niacin Mg 10.5 mg Folic Acid 200 Vitamin B6 Mg 1.5 mcg Vitamin B12 Mcg 3 **Biotin** 150 mcg Pantothenic Acid Mg 5.25 **Phosphorus** mg 250 lodine 56 100 Mcg Magnesium mg Zinc 9 Selenium 19 Mg mcg 0.75 Manganese 1 Copper Mg mg Chromium 15 Molvbdenum 45 Mca mca Chloride 435 (12.3) L-Carnitine 37.5 mg (mEq) mg **Taurine** 37.5 Choline 170 Mg mg Water 193 mL

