# 11.2 Impact Peptide 1.5 Nutrition Information - *Unflavored* (Nestlé Healthcare Nutrition)

One bottle equals 250 mL (1 Carton is 8.45 ounces)

cal g g	375 7.8 1.225	Total Fat * MCT/LCT ratio	g 50	15.9
g		MCT/LCT ratio	50	
	1 225		50:50	
	1.220	Sodium	mg	292
mg	468	Carbohydrate	g	35
g	23.5	Vitamin A	IU	3750
mg	250	Calcium	mg	250
mg	4.5	Vitamin D	IU	200
IU	25	Vitamin K	mcg	18.7
mg	0.75	Riboflavin (Vitamin B 2 )	mg	0.6
mg	7	Vitamin B6	mg	1
mcg	2	Biotin	mcg	100
mg	3.5	Phosphorus	mg	250
mcg	40	Magnesium	mg	105
mg	9	Selenium	mcg	25
mg	0.75	Manganese	mg	1
mcg	35	Molybdenum	mcg	55
mg	435	Choline	mg	138
mcg	135	L-Carnitine	mg	37.5
mg	70			
	mg g mg mg IU mg mcg mcg mg mcg mg mcg mcg mcg mcg	mg 468 g 23.5 mg 250 mg 4.5 IU 25 mg 0.75 mg 7 mcg 2 mg 3.5 mcg 40 mg 9 mg 0.75 mcg 35 mcg 35 mcg 435 mcg 135	mg 468 Carbohydrate g 23.5 Vitamin A mg 250 Calcium mg 4.5 Vitamin D IU 25 Vitamin K mg 0.75 Riboflavin (Vitamin B2) mg 7 Vitamin B6 mcg 2 Biotin mg 3.5 Phosphorus mcg 40 Magnesium mg 9 Selenium mg 0.75 Manganese mcg 35 Molybdenum mg 435 Choline mcg 135 L-Carnitine	mg 468 Carbohydrate g g 23.5 Vitamin A IU mg 250 Calcium mg mg 4.5 Vitamin D IU IU 25 Vitamin K mcg mg 0.75 Riboflavin (Vitamin B2) mg mg 7 Vitamin B6 mg mcg 2 Biotin mcg mg 3.5 Phosphorus mg mcg 40 Magnesium mg mg 9 Selenium mcg mg 0.75 Manganese mg mcg 35 Molybdenum mcg mg 435 Choline mg mcg 135 L-Carnitine mg

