6.3 Derived Variables

The following derived variables have been initially identified as important for the analysis of the safety and efficacy endpoints. It is expected that additional variables will be required. The SAP will not be amended for additional variables that are not related to the primary target or key secondary target variables. Any additional derived or computed variables will be identified and documented in the SAS programs that create the analysis files. If the SAP is not amended, further derivations related to primary and secondary target variables will be described in the CSR.

- Baseline = the last non-missing measurement before the date of RELiZORB administration for safety assessments. For efficacy assessments, baseline will be the assessment collected at Visit 2 (Day 0). However, if the result from Visit 2 is missing and the result from Visit 1 is available, the result from Visit 1 will be used.
- Study Entry = Day -14, which occurs during Study Visit 1.
- Study day = Assessment Date Date of first RELiZORB administration (+ 1 if assessment date is on or after date of first RELiZORB administration).
- Change from Baseline = Value at Post Baseline Value at Baseline.
- % Change from Baseline = 100 * Change from Baseline / Value at Baseline.
- "End of Study" is the point at which the last contact with the subject during the protocolspecified schedule is made.
- "Screen Failure" is a subject who has not met eligibility criteria.

The years of enteral tube feeding will be calculated from the first date of gastrostomy tube placement in the medical history to the Visit 1 date. For partial dates, if the day is missing, the first will be used. If the month and day are missing, January 1 will be used. The years will be calculated as (Visit 1 date – date of gastrostomy tube placement)/365.25.

The following subgroups will be used for subgroup analyses of selected endpoints:

- Age Categories: <=12 years, 13-18 years, and >=19 years.
- CFRD Categories: CRFD and non-CFRD. CFRD will include all subjects who
 reported "cystic fibrosis related diabetes", "CFRD", "type 1 diabetes mellitus",
 "diabetes mellitus related to cystic fibrosis" in their medical history.

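### Rises in plasma vitamins A and E from Day 0 cannot be read as better fat absorption, because at equal volume the treatment formula carries about 2.3 times the vitamin A and 2.2 times the vitamin E of the run-in formula

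*SAP*

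**What the plan says.** Objective 1 in Protocol 2.3 is to demonstrate increased fat absorption. Besides plasma LCPUFA levels, it names as evidence "tissue accretion (RBC) of omega-3 fatty acids such as DHA and EPA, and increased concentrations of fat soluble vitamins". The protocol synopsis, under Objective, adds: "Plasma fat-soluble vitamin and serum protein concentrations will also be measured as indicators of effectiveness".

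SAP 2.2.2 classes the vitamins as exploratory. SAP 8.3 sets the analysis: "The values for the following endpoints will be analyzed using the same MMRM comparing baseline to Day 90 on the ITT population". The list that follows includes "Plasma concentration of fat soluble vitamins (A, D and E", and the vitamin analysis is repeated by age subgroup.

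Both documents take Day 0 as baseline. Protocol 7.8: "The mean value from samples obtained on Day 0 will be used as the baseline for comparison". SAP 6.3: "For efficacy assessments, baseline will be the assessment collected at Visit 2 (Day 0", with Visit 1 used only if the Visit 2 result is missing.

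Under Protocol 4.3, Day 0 follows at least 5 days on Peptamen 1.5 within a 7-day run-in. Impact Peptide 1.5 with Relizorb then runs to Day 90 under the same volume rule. Protocol 7.3 states that the study is not randomized, and there is no comparison group.

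**The concern.** The device and the formula change on the same day. If the new formula supplies more of a vitamin, the plasma level can rise with no change in the fraction absorbed. A before-after contrast from Day 0 then measures intake and absorption together.

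The appendices show this for vitamins A and E but not for D. Neither the analysis section nor SAP section 10 mentions the difference, and the model has no intake term. A nominally significant rise in A or E could therefore be reported as support for objective 1 when the formula alone might have produced it.

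**Working it through.** **Inputs.** Contents per 250 mL come from Protocol 11.1 (Peptamen 1.5, run-in) and 11.2 (Impact Peptide 1.5, treatment). The volume of 500 to 1000 mL per feeding comes from the synopsis and Protocol 4.9.10. The plan states no vitamin intake ratio or vitamin effect size, so it offers no figure of its own to reproduce; its only power statement concerns DHA.

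**The vitamin E entry.** Protocol 11.1 gives "Vitamin D IU 200 Vitamin E IU 11.3 Vitamin K 30". In the text available for 11.2, the row labels on the left of the table are missing, and the column of values reads "mg 468 g 23.5 mg 250 mg 4.5 IU 25 mg 0.75 mg 7". The 25 IU entry is taken as vitamin E for three reasons: its unit is IU, it falls between vitamin D and vitamin K as vitamin E does in 11.1, and alpha-tocopheryl acetate is among the listed ingredients. Vitamins A and D are labelled in both tables.

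**Step 1: ratio of formula content** = Impact Peptide amount / Peptamen amount.

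| Vitamin | Peptamen 1.5 (IU/250 mL) | Impact Peptide 1.5 (IU/250 mL) | Ratio |
|---|---|---|---|
| A | 1615 | 3750 | 3750/1615 = 2.32 |
| E | 11.3 | 25 (label inferred) | 25/11.3 = 2.21 |
| D | 200 | 200 | 200/200 = 1.00 |

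**Step 2: added amount per feeding** = difference per 250 mL × 2 (500 mL) or × 4 (1000 mL).

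- Vitamin A: 2135 × 2 = 4270 IU, to 2135 × 4 = 8540 IU
- Vitamin E: 13.7 × 2 = 27.4 IU, to 13.7 × 4 = 54.8 IU
- Vitamin D: 0 IU

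**Step 3: is this only because the treatment formula has more fat?** Total fat is 14 g versus 15.9 g per 250 mL. Per gram of fat:

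- Vitamin A: (3750/15.9)/(1615/14) = 2.04
- Vitamin E: (25/15.9)/(11.3/14) = 1.95

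The extra fat explains little of the difference.

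**Step 4: dilution by other sources.** The documents do not give intake from food and supplements. Assume these supply *b* times the run-in formula amount, unchanged between periods. The ratio of total intake is then (r + b)/(1 + b), where r is the formula ratio.

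| b (assumed) | 0 | 1 | 2 | 5 | 10 |
|---|---|---|---|---|---|
| Vitamin A | 2.32 | 1.66 | 1.44 | 1.22 | 1.12 |
| Vitamin E | 2.21 | 1.61 | 1.40 | 1.20 | 1.11 |

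The ratio shrinks but stays above 1. For vitamin D it is 1.00 at every b.

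**Step 5: can anything in the plan separate intake from absorption?** The Day -14 to Day 0 comparison in Protocol 7.8 cannot, because both samples precede the switch to Impact Peptide. The per-protocol analysis does not, because every subject changes formula. No group takes Impact Peptide without Relizorb.

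**The case against.** **The endpoints carry little weight.** The formal objectives in Protocol 3.1 and SAP 2.1 tie absorption biomarkers to fatty acids and give the vitamins a separate, neutral bullet. The SAP makes them exploratory with nominal p-values. This is right, and it limits the consequence: no primary or secondary result depends on this point. But objective 1 in Protocol 2.3 still names vitamin rises as evidence, and SAP 8.3 still tests them.

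**The ratios are not intake ratios.** This also stands. Diet is unrestricted, eligibility requires feeds only four to five times a week, and supplements are not quantified. Day 0 reflects just 5 to 7 days of Peptamen after a usual formula whose vitamin content is not given. In addition, 37% of Peptamen's vitamin A activity is beta-carotene; the Impact Peptide share is not given, so a ratio for preformed vitamin A cannot be computed. These limits make the size uncertain. They do not remove the confounding.

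**Vitamin D then looks like a clean test.** A reader might infer that its equal content makes the D contrast usable as absorption evidence. The documents do not support that. The contrast is still uncontrolled, with free diet and continued medication. The formula's fat also changes: non-MCT fat goes from 14 − 10 = 4 g to 15.9 × 0.5 = 7.95 g per 250 mL. Equal dose removes one confounder only.

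**The vitamins share a line and a table.** A reader might infer a pooled vitamin test. SAP 8.3 describes no composite, and D will have its own estimate.

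**Conclusion.** The concern holds for vitamins A and E. At equal volume, the formula supplies 2.32 times the vitamin A and 2.21 times the vitamin E after the switch, and the plan cannot tell that apart from better absorption. The bias favours the device. This rests on the appendix contents, on similar volumes in the two periods, on unchanged intake from other sources and, for E, on the inferred row label. The vitamin A finding stands without E.

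A reader might infer that total intake doubles, or want a false-positive rate. Neither can be supported: other intake is not quantified, and the documents give no vitamin standard deviation and no relation between dose and plasma level. The result is a limit on what two exploratory contrasts may be used to claim.

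**What to change.** - **SAP 8.3, vitamins A and E:** state that the contrasts from Day 0 are reported descriptively, as changes under a more than doubled formula dose, and are not cited as evidence of fat absorption for objective 1.
- **SAP 8.3, vitamin D:** describe it only as the one vitamin contrast not confounded by formula dose, still subject to the limits of an uncontrolled before-after comparison.
- **Beside Tables 14.2.1.9a and 14.2.1.9b:** show formula intake of vitamins A, D and E (IU/day) for the run-in and treatment periods, as recorded volume × appendix content. Treatment volume per feeding day is already derived under SAP 9.7. Pre-treatment feeding goes into Listing 16.2.4.1. If run-in volume is not held separately, use the usual volume recorded in the observation period and say so. Note that the table leaves out food and supplements.
- **SAP section 10:** record the change. No protocol amendment is needed.
- **Check:** confirm the Impact Peptide vitamin E value in the PDF.

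The cost is SAP wording and one derived table, with no new data collection. The downside is that two exploratory results no longer support the efficacy claim.

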8.3.1 Weight Gain Velocity

Weight gain velocity changes from historical average (baseline) to 0-90 days by age subgroup will be assessed by a one-sample t-test if the test for normality by Shapiro-Wilkes is met, or otherwise by the Wilcoxon signed rank test.

8.3.2 Weight and BMI Z-scores

Age-specific z-scores for weight and BMI are obtained (via CDC standard tables) at each study visit and at quarterly intervals in the year prior to baseline. For weight and for BMI, the average historical distribution percentile (mean of historical values) and the z-scores (and distribution percentile) at 30, 60 and 90 days will be presented. The change in percentile of the distribution from historical average to 90 days will be tested by a one-sample t-test or Wilcoxon signed rank test. This analysis will be performed by age subgroup only.

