# **Endpoints**

### Efficacy

- Change over time in plasma concentrations of omega-3 fatty acids such as DHA and EPA
- Change over time in tissue (erythrocyte membrane) fatty acid concentrations such as DHA and EPA
- Change over time in the plasma fatty acid profile
- Change over time in the ratio of omega-6 to omega-3 fatty acids
- Change over time in plasma concentrations of fat soluble vitamins A, D, and E
- Change over time in serum protein concentrations (total protein, prealbumin, albumin, transferrin)
- Change over time in markers of inflammation (urinary leukotrienes)
- Change over time in weight and body mass index (BMI) and weight and BMI z-scores

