2.2.2 Efficacy Endpoints

The primary efficacy variable is the composition changes (%) of total DHA plus EPA (omega-3 index) in erythrocyte membranes.

The secondary efficacy endpoints include changes in:

- Erythrocyte membrane composition (%) of total DHA
- Erythrocyte membrane composition (%) of total EPA
- Erythrocyte membrane composition (%) ratio of omega-6 to omega-3 fatty acids
- Plasma concentration of total DHA concentration (μg/mL)
- Plasma concentration of total EPA concentration (µg/mL)
- Plasma concentration of total DHA+EPA concentration (μg/mL)
- Plasma composition (%) ratio of omega-6 to omega-3 fatty acids

The exploratory efficacy endpoints include:

- Plasma concentrations of fat soluble vitamins A, D and E
- Serum protein concentrations (total protein, pre-albumin, albumin, transferrin)
- Marker of inflammation (urinary leukotriene LTE₄)
- Weight gain velocity versus historical comparison
- Standardized Body weight and BMI expressed as age-specific z-score via CDC reference.

Plasma concentrations (µg/mL) of total DHA and total EPA measured by ultra high performance liquid chromatography (UHPLC) will be provided by Total EPA+DHA will be calculated as the sum of the concentrations of total DHA and total EPA. Fatty acid composition (%) in both plasma and erythrocytes is measured by gas chromatographymass spectrometry (GCMS) and is provided by

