6.3.1.2 Weight and BMI Z-scores and Percentiles Derived Variables

Weight and BMI values from baseline (Visit 2 or Visit 1 if Visit 2 is missing) and Visit 3 to Visit 5 will be normalized to Z-scores based on age- and sex-specific data from the Centers for Disease Control and Prevention (CDC). A SAS program and dataset obtained from the CDC website will be used to calculate the values for healthy subjects aged 2-20 years, with age expressed in months with decimal. The CDC data is provided in half month intervals for age.

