14.2.1.7	ITT	Changes over Time in Serum Protein Concentrations (Total Protein, Prealbumin, Albumin, and Transferrin)	16.2.5.6.1
14.2.1.8	ITT	Changes over Time in Urinary Leukotriene E4	16.2.5.7.1
14.2.1.9a	ITT	Changes over Time in Plasma Concentrations of Fat Soluble Vitamins (A, D, and E)	16.2.5.5.1
14.2.1.9b	ITT	Changes over Time in Plasma Concentrations of Fat Soluble Vitamins (A, D, and E) by Age Subgroup	16.2.5.5.1
14.2.1.10	ITT	Weight and Body Mass Index (BMI) Z-scores by Age Subgroup and Comparison to Historic Z-score	16.2.5.10.1
14.2.1.11	ITT	Changes over Time in Weight Gain Velocity (g/kg/90 days) Compared to Historical by Age Subgroup	16.2.5.9.1
14.3.1.1	Safety	Summary of Adverse Events	16.2.6.1, 16.2.6.2, 16.2.6.3, 16.2.6.5
14.3.1.2	Safety	Adverse Events by System Organ Class and Preferred Term	16.2.6.1
14.3.2.1	Safety	Unanticipated Adverse Device Effects by System Organ Class and Preferred Term	16.2.6.3
14.3.2.2	Safety	Unanticipated Adverse Device Effects by System Organ Class, Preferred Term, and Relationship	16.2.6.3
14.3.2.3	Safety	Unanticipated Adverse Device Effects by System Organ Class, Preferred Term, and Severity	16.2.6.3

Table Number	Population	Title	Listing Reference
14.3.3.1	Safety	Gastrointestinal Symptom Diary: Frequency and Incidence – Overall and by Symptom	16.2.7.1
14.3.4.1	Safety	Summary of Clinical Chemistry Measurements: Results and Change from Baseline	16.2.8.1
14.3.4.2	Safety	Summary of Hematology Measurements: Results and Change from Baseline	16.2.8.2
14.3.4.3	Safety	Summary of Numeric Urinalysis Measurements: Results and Change from Baseline	16.2.8.3
14.3.4.4	Safety	Summary of Blood Lipids: Results and Change from Baseline	16.2.8.4
14.3.5.1	Safety	Summary of Vital Sign Measurements: Results and Change from Baseline	16.2.9.1
14.3.6.1	Safety	Concomitant Medications	16.2.3.3

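### The SAP defines the exploratory growth endpoint as a weight and BMI z-score but tests the change in percentile, a scale that gives less weight to subjects with low z

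*SAP*

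**What the plan says.** **Endpoint.** SAP 2.2.2 lists among the exploratory efficacy endpoints "Standardized Body weight and BMI expressed as age-specific z-score via CDC reference". The protocol synopsis lists "Change over time in weight and body mass index (BMI) and weight and BMI z-scores", so it names raw weight and BMI as well as z-scores.

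**Derivation.** SAP 6.3.1.2 converts weight and BMI to z-scores against CDC age- and sex-specific reference data, for baseline and Visits 3 to 5. Its heading also mentions percentiles, but its text does not define one. SAP 6.3.1 collects up to four historical weight, height and BMI recordings, with BMI percentile for subjects aged 18 or under.

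**Analysis.** SAP 8.3.2, headed as a z-score section, says that z-scores are obtained at each study visit and quarterly in the year before baseline. It summarises history as the mean of the historical percentiles and adds that "the z-scores (and distribution percentile) at 30, 60 and 90 days will be presented". It then gives one test: "The change in percentile of the distribution from historical average to 90 days will be tested by a one-sample t-test or Wilcoxon signed rank test". Finally, "This analysis will be performed by age subgroup only".

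**Output.** Table 14.2.1.10 is titled "Weight and Body Mass Index (BMI) Z-scores by Age Subgroup and Comparison to Historic Z-score".

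SAP section 10, which lists changes from the protocol's planned analysis, does not mention the choice of percentile.

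**The concern.** SAP 8.3.2 names z-score and percentile side by side as separate quantities, so percentile there cannot be loose wording for z-score. Read literally, the endpoint is defined and tabulated on one scale and tested on another, and no test of the z-score is specified anywhere.

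The two scales are not interchangeable for a mean change. The percentile curve is steep near the median and flat in the tails, so equal z gains count unequally according to where the subject starts. Protocol 2.3 describes enteral feeding as support for nutritionally challenged patients with pancreatic insufficiency, so some subjects may plausibly have low z. Those subjects would contribute least to the test of growth.

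**Working it through.** **The plan's own figure.** Neither document gives a power or effect size for weight or BMI. The only sample-size statement (30 evaluable subjects, effect size 0.53, 80% power) reproduces as 80.1% with a paired t-test at two-sided 0.05. It concerns DHA and does not bear on this point.

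**Step 1: the transform.** I take percentile = 100·Φ(z), with Φ the standard normal distribution function. The weight of a small z change, relative to the same change at z = 0, is exp(-z²/2).

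| Starting z | Percentile | Points for +0.3 z | Relative weight |
|---|---|---|---|
| 0 | 50.0 | 11.8 | 1.00 |
| -0.5 | 30.9 | 11.2 | 0.88 |
| -1 | 15.9 | 8.3 | 0.61 |
| -1.5 | 6.7 | 4.8 | 0.32 |
| -2 | 2.3 | 2.2 | 0.14 |
| -2.5 | 0.6 | 0.8 | 0.04 |
| -3 | 0.1 | 0.2 | 0.01 |

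**Step 2: can the sign differ?** The transform is increasing, so if every subject gains, both means are positive. A difference in sign needs changes that vary with starting z. Two illustrations with assumed values:

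- Two subjects, z from -2.0 to -1.6 and from 0 to -0.1. Mean z change = (0.4 - 0.1)/2 = +0.15. Percentile changes are 5.48 - 2.28 = +3.20 and 46.02 - 50 = -3.98, with mean -0.39.
- Six subjects starting at -2.5, -2.0, -2.0, 0, 0.2 and -0.1, with z changes +0.5, +0.4, +0.4, -0.2, -0.2 and -0.2. Mean z change is +0.12; mean percentile change is -2.6 points. The signed-rank sums go from W+ = 15, W- = 6 on z to W+ = 6, W- = 15 on percentile, so the Wilcoxon option does not protect against this.

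**Step 3: when does it happen in a group?** Simulated starting z is normal with SD 1, and the mean z change is +0.10. The slope is the extra z change per unit of starting z.

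| Mean starting z | Slope 0 | Slope -0.15 | Slope -0.30 |
|---|---|---|---|
| -1.5 | +1.7 | -0.1 | -1.9 |
| -1 | +2.3 | +0.7 | -0.9 |
| -0.5 | +2.7 | +1.9 | +1.0 |
| 0 | +2.8 | +3.0 | +3.3 |

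Entries are mean percentile changes. With a uniform gain the sign always holds. It reverses only where the mean starting z is -1 or lower and the gain falls steeply enough with starting z that heavier subjects lose.

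**Step 4: power without reversal.** Assumed z change has mean 0.2 and SD 0.35, unrelated to starting z. The test is a one-sample t-test with n = 10, which is 30 subjects split evenly over the three age groups of SAP 6.3.

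| Mean starting z | Power on z | Power on percentile |
|---|---|---|
| -1.5 | 37% | 25% |
| -1 | 36% | 31% |
| -0.5 | 37% | 34% |
| 0 | 37% | 32% |

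**Step 5: averaging history.** A mean of percentiles is not the percentile of the mean z. Historical z of -2.2, -2.0 and -1.8 gives 2.42 against 2.28, which is trivial. Widely spread values of -2.5, -1.5, -1.5 and -0.5 give 11.2 against 6.7. For a subject whose z is steady over the year, this part hardly matters.

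**The case against.** The endpoint is exploratory, p-values are nominal, z-scores are still presented at Days 30, 60 and 90 and listed by subject, and growth is also tested through weight gain velocity, which has no percentile compression. Percentile is not alien to the plan either: SAP 6.3.1 collects BMI percentile and the heading of 6.3.1.2 names it. The shell of Table 14.2.1.10 is not in the text available to me and might contain a z-score comparison. All of this stands and keeps the point modest. None of it supplies a test on the defined endpoint or a reason for testing something else.

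Three stronger readings are tempting and are not supported:

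- *Underweight subjects barely count.* That fits only z of about -2 or lower (relative weight 0.14 or less). At z = -1 the weight is still about 0.61. The inclusion criteria set no weight or BMI limit, and an established tube-fed population need not sit at -2.
- *The test will point the wrong way.* Reversal needs gains in lighter subjects together with smaller gains and, for at least some subjects, losses nearer the median. The worked cases in step 2 are constructed to show that it is possible, not that it is likely.
- *A z-score test planned in the protocol was replaced.* Protocol 7.8 builds its standard score from the subject's own historical and Day 0 recordings, does not mention CDC data, and names no test for that score. The conflict is mainly within the SAP.

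**Conclusion.** The mismatch is plain in the text. SAP 2.2.2 and the title of Table 14.2.1.10 are on the z-score scale, and the single test in SAP 8.3.2 is on the percentile scale, with no reason given.

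The unequal weighting follows from the transform: the same 0.3 z gain counts about five times as much at z = 0 as at z = -2 (11.8 against 2.2 points). The practical loss depends on a baseline distribution that the documents do not give. Under the assumptions in step 4 it is 12 percentage points of power at a mean starting z of -1.5 and about 3 to 5 points at -1, -0.5 or 0. A change of sign is possible only under the pattern described above. The primary and secondary results are not affected. The correction is worth making because it puts the test on the defined endpoint at almost no cost.

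**What to change.** In SAP 8.3.2, apply the one-sample t-test or Wilcoxon signed rank test already named to the Day 90 z-score minus the mean of the subject's historical z-scores, for weight and for BMI separately. Keep percentiles as descriptive columns, where they remain useful to clinical readers. In SAP 6.3.1.2, list the historical weights and BMIs among the values converted to z-scores, so that it agrees with 8.3.2.

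The cost is short edits to two SAP sections and the matching program. No new data are needed: the historical weights, heights and BMIs are already collected, and the CDC program already produces z-scores. The title of Table 14.2.1.10 can stay.

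The CDC program covers ages 2 to 20 only. That limits what can be computed in the oldest age group, but it applies equally to percentiles and z-scores, so this change neither causes nor cures it.
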